9.6	R	Reporting Procedures for All Adverse Events	43
9.	6.1	Reporting Procedures for Serious AEs	44
9.	6.2	Reporting Procedures for SUSARS	44
9.	6.3	Development Safety Update Report	44
9.7	Д	Assessment of severity	44
9.8	Р	Procedures to be followed in the event of abnormal findings	46
9.9	L	ocal Safety Committee	46
9.	9.1	Safety Profile Review	47
9.10) S	afety Holding Rules	47
10	STA	ATISTICS	48
11.	QU	ALITY CONTROL AND QUALITY ASSURANCE PROCEDURES	50
11.1	L II	nvestigator procedures	50
11.2	2 N	Aonitoring	50
11.3	8 N	Aodification to protocol	50
11.4	ŀΡ	Protocol deviation	50
11.5	5 Α	Audit & inspection	50
11.6	5 S	erious Breaches	51
11.7	7 Т	rial Progress	51
11.8	8 P	Publication Policy	51
12.	ETH	HICS AND REGULATORY CONSIDERATIONS	53
12.1	LC	Declaration of Helsinki	53
12.2	2 0	Guidelines for Good Clinical Practice	53
12.3	B li	nformed Consent	53
12.4	ĻΑ	Approvals	53
12.5	5 V	/olunteer Confidentiality	53
13.	DA	TA HANDLING AND RECORD KEEPING	54

13.1	Data Handling	54
13.2	Record Keeping	54
13.3	Source Data and Case Report Forms (CRFs)	54
13.4	Data Protection	54
14 F	INANCING AND INSURANCE	55
14.2	Financing	55
14.3	Insurance	55
14.4	Compensation	55

Title	A phase I study to determine the safety and immunogenicity of the candidate influenza vaccine MVA-NP+M1, manufactured on the AGE1.CR.pIX novel avian cell line, in healthy adult volunteers.					
Trial Centres		Centre for Clinical Vaccinology & Tropical Medicine, University of Oxford, Churchill Hospital, [name].				
Trial Identifier	FLU008					
Clinical Phase	I					
Design	Open label, phase I clin	ical trial.				
Target Population	Healthy adults aged 18	to 50				
Sample Size	Total: 6					
	Group	Dose				
	Group 1 (n=6) Aged 18-50	1.5 x10 ⁸ pfu (converted from TCID ₅₀) MVA-NP+M1 alone				
Follow-up duration	4 weeks					
Planned Trial Period	Q3 2017 – Q4 2017					
Primary Objectives	To assess the safety of MVA-NP+M1, manufactured on the AGE1.CR.pIX novel avian cell line.					
Secondary Objectives	To assess the cellular immune response generated by the MVA-NP+M1, manufactured on the AGE1.CR.pIX novel avian cell line.					
Investigational products	MVA-NP+M1					
Form	Liquid					

Route of	Intramuscular (IM) injection into the Deltoid
Administration	

Dose per1.5 x10⁸ pfu (converted from TCID₅₀)Administration

2. ABBREVIATIONS

AE	Adverse event
ССVТМ	Centre for Clinical Vaccinology and Tropical Medicine, Oxford
CBF	Clinical BioManufacturing Facility
CEF	Chick embryo fibroblast
CI	Chief Investigator
CRF	Case Report Form or Clinical Research Facility
DSUR	Development Safety Update Report
ELISPOT	Enzyme-linked immunospot
GCP	Good Clinical Practice
GMO	Genetically modified organism
GP	General Practitioner
HCG	Human Chorionic Gonadotrophin
HBV	Hepatitis B virus
HCV	Hepatitis C virus
HIV	Human immunodeficiency virus
IB	Investigator Brochure
ICH	International Conference on Harmonisation
ID	Intradermal
IFNγ	Interferon gamma
IM	Intramuscular
IMP	Investigational Medicinal Product
IMP-D	Investigational Medicinal Product Dossier
IV	Intravenous
LSM	Local safety monitor
MHRA	Medicines and Healthcare Products Regulatory Agency
MVA	Modified vaccinia virus Ankara
NHS	National Health Service
РВМС	Peripheral blood mononuclear cell
pfu	Plaque forming unit
QP	Qualified Person
REC	Research Ethics Committee
SAE	Serious adverse event
SOP	Standard Operating Procedure

SUSAR	Suspected unexpected serious adverse reaction
TCID ₅₀	Median tissue culture infective dose
WHO	World Health Organisation

3. BACKGROUND AND RATIONALE

3.1 The need for a new vaccine against influenza

Influenza is an orthomyxovirus and encodes a segmented RNA genome. Influenza is divided into 3 groups- A, B and C. Most seasonal influenza and all known pandemics are caused by Influenza A, whilst B and C cause low-levels disease and sporadic outbreaks (1). Influenza A is subdivided further on the basis of hemagglutinin (H or HA) and neuraminidase (N or NA) activity- for example, H1N1 subtype. There are at least 16 different types of HA and 9 of NA. These proteins are found as spiked surface projections on the Influenza A virus (2). Other genes encode proteins vital for structure, reproduction and virulence including nucleoprotein (NP), Matrix 1 (M1), M2 (ion pore), NS1, NS2, PA, PB1, PB1-F2 and PB2, which are found within the envelope (1, 2).

Seasonal influenza has a huge annual global impact accounting for an estimated 1 billion illnesses and 250,000 – 500,000 deaths (3) with an economic cost of annual seasonal influenza estimated to be \$87.1 billion in the US alone (4). Influenza pandemics also occasionally occur, leading to increased significant health and economic burden (5). The unpredictable risk of sporadic outbreaks of human infections with avian influenza (H5N1), which could trigger a new pandemic if the virus acquires the ability to transmit from person to person, (6) makes influenza a major global public health issue. Young children, the elderly, pregnant women and those with significant co-morbidities such as asthma, chronic respiratory disease and immunosuppressive conditions remain at highest risk of influenza infection.

Vaccination remains the most cost-effective strategy available to combat influenza. The currently available influenza vaccines work in part by inducing strain-specific antibodies against the highly polymorphic surface proteins (hemagglutinin, neuraminidase) of the influenza virus. Inactivated or live vaccines are made up of proteins or live viruses covering four influenza virus strains (H1N1, H3N2 and two strains of influenza B) which are predicted to circulate in the population in the upcoming influenza season. As the circulating virus strains change, influenza vaccines need to be reformulated annually to match new strains arising from genetic drifts on the surface proteins of these seasonal viruses. These surface proteins, to which vaccine-induced antibodies are targeted, are highly polymorphic. There is little protection against strains of a new subtype and limited protection even across strains within the same subtype. Approximately once every 20 years, vaccine efficacy happens to be much lower than expected due to significant antigenic drifts away from the vaccine strain (7). This need for constant redesign and remanufacture increases the vaccine's cost, places limitations on supply (8) and critically delays vaccine production. When new strains arise, the HA and NA sequences need to be identified and incorporated into the new vaccine, leaving large populations susceptible to infection and illness from the new strains. However, not only is the efficacy of current vaccines limited in the face of antigenic mismatch between circulating strains and those in the vaccine but it is also substantially reduced in elderly groups. Vaccination in older adults prevents laboratory-confirmed influenza in only 30–40% compared to the 70–90% protection found in young adults (9). Thus, there is an unmet need for improved vaccination strategies that can provide protection against a broader spectrum of virus strains particularly for the elderly.

Where individuals exposed to a newly arisen influenza virus strain lack protective neutralising antibodies, cross-reactive T-cells against conserved internal antigens of influenza have been shown to be associated with limited viral shedding, reduced duration of symptoms and minimised severity of symptomatic illness (10, 11). Thus, an influenza vaccine capable of inducing protective T cell responses against conserved internal antigens could provide lasting immunity against not only human seasonal influenza, but also subtypes currently found in avian species or swine (which could potentially cause new pandemics). Since adults have been primed by previous influenza exposure, a vaccine expressing conserved internal antigens of influenza (such as NP and M1) could be used to boost cross-reactive T-cell responses to protective levels, providing durable broad immunity to all subtypes of influenza A.

Recombinant viral vectored vaccines have been used in humans to induce high frequencies of CD4+ and CD8+ T cell responses to a wide range of antigens. One such recombinant viral vector is the Modified Vaccinia Ankara (MVA) which has been used to generate strong T-cell responses to a wide range of antigens, including antigens from plasmodium, tuberculosis, hepatitis C, HIV and influenza. The MVA-NP+M1 is a recombinant replication-deficient MVA vector expressing the influenza antigens NP and M1 as a fusion protein (12).

Vaccination with MVA-NP+M1 leads to a rapid increase of influenza-specific cross-reactive IFN- γ -secreting effector T cells, which are maintained at protective levels over a prolonged period(12). In the older age groups, MVA-NP+M1 can boost pre-existing levels of influenza-specific T-cells and maintain them for up to six months post-vaccination (13). The MVA-NP+M1 combined with a licensed inactivated influenza vaccine induced influenza-specific T-cells and increased the magnitude and breadth of the antibody response induced by the inactivated influenza vaccine (14). Furthermore, in a Phase IIa challenge study of MVA-NP+M1 alone, vaccinated individuals experimentally challenged with live influenza virus had less severe symptoms and significantly shorter duration of viral shedding compared to unvaccinated controls (15). Taken together, these studies demonstrate the efficacy of MVA-NP+M1 in limiting the severity of influenza illness and its higher immunogenicity in older adults when combined with a licensed inactivated seasonal influenza vaccine.

3.2 Previous experience with MVA vectored vaccines.

MVA is an attractive candidate orthopox vaccine vector for safety and immunogenicity reasons. The successful worldwide eradication of smallpox using vaccination with the vaccinia virus highlighted it as a candidate vaccine vector. Although millions of humans have

been vaccinated with conventional replication-competent vaccinia virus, its small but definite risk to both researchers and future patients led to the development of several attenuated strains of vaccinia during early smallpox eradication strategies and more recently as well. The host-range restricted MVA particularly proved to be extremely attenuated compared to other vaccinia viruses.

MVA was originally derived from the vaccinia strain Ankara by over 500 serial passages in primary chicken embryo fibroblasts (CEF cells). MVA has six major genomic deletions compared to the parental Ankara genome and is severely compromised in its ability to replicate in mammalian cells. No replication has been documented in non-transformed mammalian cells. The viral genome has been proven to be stable through a large series of passages in chicken embryo fibroblasts (16). MVA also showed no cytopathic effect or plaque formation in cells of human origin. In irradiated mice, it did not elicit any morbidity or lethality even when administered at high doses intra-cerebrally, indicating its safety even in immuno-compromised organisms (16).

MVA has an excellent safety record and it has been administered to approximately 120,000 people during a smallpox eradication campaign in a field study in Germany in the 1970s (17). MVA is currently in development as a vector for multiple diseases including HIV-1, (18, 19) tuberculosis, (20) HCV (21), influenza (12) and melanoma (22). The MVA vectored vaccines developed at the University of Oxford have been administered to over 4570 individuals including infants, young children, elderly adults, HIV-infected adults and children and patients with cancer in Europe and Africa without any safety concerns. Clinical studies have shown intramuscular administration, as compared to intradermal, to be associated with fewer and short-lived local AEs and no reduction in immunogenicity (23).

3.3 The novel avian cell line AGE1.CR.pIX

There are a number of disadvantages to using CEF cells for the production of MVA vectored vaccines including limited scalability of the process, possible shortage of material in case of an avian pandemic and occasional difficulties with bacterial contamination of embryonated eggs. Therefore, the MVA-NP+M1 for use in this study is being produced in the novel immortalised duck retinal cell line AGE1.CR.pIX grown in a serum-free medium. This cell line was designed according to the current regulatory requirements and was optimized to address the scalability limitations imposed by the CEF manufacturing process.

The avian cell line AGE1.CR (CR) was created by immortalizing cells from duck retina with adenovirus type 5 E1 genes. Ducks as opposed to chickens carry significantly fewer endogenous retroviral inserts, meaning the novel cell line is also safer than previous attempts to use cell lines derived from spontaneous immortalization of embryonic chicken cells. The CR line was further modified for constitutive expression of the adenoviral pIX gene (to obtain CR.pIX) that encodes for a structural protein involved in capsid stabilization of cognate adenovirus. CR and CR.pIX cell lines proliferate in suspension in serum-free media.

Exceptional genetic stability was demonstrated for more than 90 passages. The cells can be productively infected with viruses of diverse families including different influenza strains and MVA (24).

The AGE1.CR.pIX avian cell line typically proliferates with an indefinite life span in suspension in serum-free medium with zero or low protein content. Immortalization is achieved by transfection of the E1A and E1B genes from the human adenovirus serotype 5. The cell lines are adapted to proliferation in suspension in media free of animal derived components. Both in adherent monolayers and in suspension culture the cells are highly permissive for MVA, surpassing yields obtained with primary chicken fibroblasts (25).

3.4 The selection of NP+M1 as an insert for a viral vectored vaccine

The inner proteins of the influenza virus are more conserved and less prone to antigenic drifts compared to the external surface glycoproteins. There are two reasons for selecting NP and M1 as a target for T-cell inducing vaccines. Firstly, there is very little polymorphism of NP and M1 across influenza A isolates. NP is 92% identical between H3N2 and H1N1 strains, and 91% identical between H3N2 and H5N1 strains. M1 is 95% identical between H3N2 and H1N1 strains, and 91% identical between H3N2 and H5N1 strains. M1 is 95% identical between H3N2 and H1N1 strains, and 93% identical between H3N2 and H5N1 strains. This low level of variation appears to allow strong T cell cross-reactivity. H3N2-derived antigen sequences (from A/Panama/2007/99) have been included as this is the subtype to which most people will have memory T cell responses. In the local population more than 70% of individuals generate a T cell response to these two antigens (26). Secondly, analysis of T-cell response to all the proteins of influenza have shown that the T-cell response to NP and M1 is the strongest and 80% of individuals have responses to these two proteins (Figure 1). Furthermore, recent studies have shown that T-cells specific to M1 and NP are associated with protecting individuals against influenza by limiting viral shedding, reduced duration of symptoms and minimising severity of symptomatic illness (10, 11).

[figure not shown]

Figure 1. Frequency and magnitude of T cell responses to influenza antigens in UK adults. Responses to M1 and M2 were tested together, but in the small number of volunteers where these were separated the response was predominantly to M1 rather than M2.

HA	hemagglutinin	NS1	non-structural protein 1
NA	neuraminidase	NS2	non-structural protein 2
M1	matrix protein 1	PB1	polymerase subunit B1
M2	matrix protein 2	PB2	polymerase subunit B2
NP	nucleoprotein	PA	polymerase subunit A

3.5 Pre-Clinical Studies

The MVA viral vector manufactured using the AGE1.CR.pIX avian cell line has been previously used with a different insert for an Ebola preventive vaccine (MVA-EBOZ). A GLP-compliant non-clinical toxicology study was conducted to evaluate the local and systemic toxicity of the MVA85A vaccine manufactured using the AGE1.CR.pIX® avian cell line. The MVA85A was used as a surrogate test article to support the use of a MVA-EBOZ vaccine produced in the AGE1.CR.pIX® avian cell line and to demonstrate the safety of the vaccine for the first in human trial. The manufacturing process to produce MVA-EBOZ was derived from that used for MVA85A. The toxicology study performed on BALB/c mice revealed that repeated administration of MVA85A had no effect on mortality, cage side observations or bodyweights. Mice gained weight and had normal food consumption during the study. Clinical observations, inoculation site reactogenicity, clinical chemistry, clinical haematology, gross necropsy, organ weights and histopathology indicated no overt toxicity related to MVA85A vaccine administration (see IB for MVA-EBOZ J).

3.6 Previous clinical experience

[figure not shown]
This is the first-in-human trial of MVA-NP+M1 produced using the AGE1.CR.pIX immortal avian cell line. However, MVA-NP+M1 manufactured using CEF cells has been administered to 145 adults in six clinical trials (5 phase I trials and 1 Phase IIa challenge study). The vaccine has been shown to have a good safety profile with no vaccine related serious adverse events during these trials. The vaccine was safe and boosted T-cell responses as expected when administered to healthy adults. A dose dependent increase in adverse events was observed and a dose of 1.5 x10⁸ pfu was found to be the optimal balance between immunogenicity and reactogenicity (12). It has also been given at the same time as the standard seasonal influenza vaccine (FLU003) and has been shown to have a good safety profile. MVA NP+M1 has already been shown to provide protection against viral shedding and severity of symptoms in a Phase IIa influenza challenge study (FLU002). In FLU002, fewer vaccinated volunteers developed influenza symptoms than the unvaccinated

volunteers and there was a statistically significant reduction in duration of virus shedding in vaccinated volunteers (15).

MVA-NP+M1 has been administered to 145 individuals across a range of doses and via both the intramuscular and intradermal routes, as shown in Table 1. Figure 2 demonstrates the immunogenicity (as determined by interferon-gamma ELISpot) of MVA-NP+M1 in older adults (aged 50+) receiving a dose of 1.5 $\times 10^8$ pfu.

Country	Study	Vaccine	Age	Route	Dose of MVA-NP+M1	Number of volunteers
		MVA-NP+M1	18-50	ID	5 x10 ⁷ pfu	12
		MVA-NP+M1	18-50	IM	5 x10 ⁷ pfu	8
UK	FLU001	MVA-NP+M1	18-50	IM	2.5 x10 ⁸ pfu	8
OK	160001	MVA-NP+M1	50-59	IM	1.5 x10 ⁸ pfu	10
		MVA-NP+M1	60-69	IM	1.5 x10 ⁸ pfu	10
		MVA-NP+M1	70+	IM	1.5 x10 ⁸ pfu	10
UK	FLU002	MVA-NP+M1	18-50	IM	1.5 x10 ⁸ pfu	15
UK	FLU003	MVA-NP+M1 (together with seasonal influenza vaccine)	50+	IM	1.5 x10 ⁸ pfu	9
UK	FLU004	ChAdOx1-NP+M1/MVA- NP+M1 (7-14 weeks apart)	18-50	IM	1.5 x10 ⁸ pfu	3
		ChAdOx1-NP+M1 / MVA- NP+M1 (8 weeks apart)	18-50	IM	1.5 x10 ⁸ pfu	12
		ChAdOx1-NP+M1 / MVA- NP+M1 (52 weeks apart)	18-50	IM	1.5 x10 ⁸ pfu	8
UK	FLU005	MVA-NP+M1 / ChAdOx1- NP+M1 (8 weeks apart)	18-50	IM	1.5 x10 ⁸ pfu	13
		MVA-NP+M1 / ChAdOx1- NP+M1 (52 weeks apart)	18-50	IM	1.5 x10 ⁸ pfu	12
		ChAdOx1-NP+M1 / MVA- NP+M1 (8 weeks apart)	>50+	IM	1.5 x10 ⁸ pfu	12
UK	FLU006	MVA-NP+M1 (co- administered with seasonal influenza vaccine - Viroflu®	18-50	IM	1.5 x10 ⁸ pfu	3

Table 1. Previous MVA-NP+M1 trials

Weeks post immunisation

Figure 2: Immunogenicity of MVA-NP+M1 in older adults (FLU001)

The EBL04, a phase I Ebola vaccine trial, was the first administration of MVA-EBO Z in humans and the first trial of any MVA bio-manufactured on an immortalised duck retinal cell line, instead of the standard chicken embryo fibroblast primary cells. The trial enrolled 38 healthy adult volunteers in the UK and follow up is still ongoing. To this date, no significant safety concerns have been reported. A few volunteers reported moderate local and systemic adverse events. One volunteer reported severe local erythema on day 4 post-vaccination. One volunteer reported severe fevers associated with severe fatigue and malaise. MVA-EBO Z was generally well tolerated, causing mild-to-moderate short-lived local and systemic adverse events. There have not been any vaccine related SAEs until this date (see development safety update report for EBL04)

3.7 Rationale

Vaccination remains the most cost-effective strategy available to combat influenza. Current influenza vaccines work by inducing strain-specific antibodies against the highly polymorphic surface proteins of the influenza virus. The need for constant redesign and remanufacture increases the vaccine's cost, places limitations on supply and critically delays vaccine production when new strains arise. Thus, there is a major demand for improved vaccination strategies that can provide protection against a broad spectrum of virus strains.

The elderly are at higher risk of severe disease and vaccination in older adults has poor efficacy, preventing only 30-40% of laboratory-confirmed influenza. Previous MVA-NP+M1 trials have shown satisfactory immunogenicity across different age groups with tolerable reactogenicity. A phase IIa influenza challenge study has shown the MVA-NP+M1 is able to

provide protection against viral shedding and to reduce severity of influenza symptoms. The MVA-NP+M1 produced in the novel immortalised duck retinal cell line AGE1.CR.pIX addresses the scalability issues of CEF produced vaccines, optimising vaccine production processes.

3.8 Vaccine development strategy

The MVA-NP+M1 is a Modified Vaccinia Ankara vectored vaccine, manufactured on the novel avian cell line AGE1.CR.pIX, expressing the conserved influenza A nucleoprotein and matrix protein. T-cell responses specific to M1 and NP, elicited by this viral vectored vaccine, are associated with protecting individuals in a human influenza challenge study by limiting viral shedding, reduced duration of symptoms and minimising severity of symptomatic illness. Previous clinical trials have shown the vaccine is satisfactory safe and immunogenic across different age groups.

The trial aims to contribute towards the development of a more efficacious vaccine capable of providing protection against a broad spectrum of influenza A virus strains with better immune responses in those at higher risk of severe influenza disease.

The MVA-NP+M1 produced in immortalised avian cell line will be used in a subsequent phase IIb clinical trial involving 2,000 volunteers, providing there are no safety concerns identified during this phase I trial.

Taking together the previous safe use of MVA-NP+M1 manufactured in CEF cells and MVA-EBOZ manufactured in AGE1.CR.pIX, there is no reason to suspect that the adverse event profile of MVA-NP+M1 manufactured in AGE1.CR.pIX will differ from that of MVA-NP+M1 manufactured in CEF cells. Conducted prior to initiating a phase IIb study in 2000 individuals in which 1000 individuals will receive MVA-NP+M1, this small phase I bridging study will allow the investigators to confirm that there is no difference in the safety profile of the vaccine as a result of a change in the cells used for production.

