4. TRIAL DESIGN

This is a first in human, phase I, open label study of the MVA viral vector (produced in the novel immortalised duck retinal cell line AGE1.CR.pIX) expressing the influenza antigens NP and M1 as a fusion protein, in healthy adult volunteers. MVA-NP+M1 will be given alone intramuscularly as a single dose.

There will be 1 study group and a total of 6 volunteers will be enrolled (table 2). Staggered enrolment will apply for the first three volunteers within the group. Volunteers will be allocated by selecting eligible volunteers for enrolment in the order in which they were deemed eligible following screening.

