5. OBJECTIVES AND ENDPOINTS

The number of volunteers has been chosen to generate adequate safety and immunogenicity data to meet these objectives

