10 STATISTICS

Sample Size Selection and Statistical analysis

This is a descriptive safety study, where volunteers will be vaccinated with MVA-NP+M1 alone. A maximum of 6 volunteers will be vaccinated in total. Safety data will be presented according to frequency, severity and duration of adverse events. This sample size should

allow an initial estimation to be made of the frequency and magnitude of outcome measures.

Non-parametric tests will be used to determine differences in the primary immunogenicity outcome (ELISpot) data, testing for differences in responses between time points within a group.

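### Section 3.8 says six uncontrolled volunteers will confirm no difference in safety after the change of production cells; a single descriptive group of 6 can only give a first estimate

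*Protocol*

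**What the plan says.** The protocol describes the purpose of the study in two ways.

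- **Section 3.8 (Vaccine development strategy)** makes a comparative claim: "this small phase I bridging study will allow the investigators to confirm that there is no difference in the safety profile of the vaccine", meaning a difference due to the new production cells. The same section places this ahead of a phase IIb trial of 2000 people, 1000 of whom will receive the vaccine.
- **Section 4 (Trial design)** sets out the design: "This is a first in human, phase I, open label study of the MVA viral vector", and "There will be 1 study group and a total of 6 volunteers will be enrolled". There is no arm given CEF-produced vaccine.
- **Section 10 (Statistics)** says: "This is a descriptive safety study, where volunteers will be vaccinated with MVA-NP+M1 alone". It adds "A maximum of 6 volunteers will be vaccinated in total", that "Safety data will be presented according to frequency, severity and duration of adverse events", and that the sample should "allow an initial estimation to be made of the frequency and magnitude of outcome measures". The only test named compares ELISpot responses between time points within the group, so it concerns neither safety nor cell line.
- **Section 5 (Objectives and endpoints)** says: "The number of volunteers has been chosen to generate adequate safety and immunogenicity data to meet these objectives". The primary objective there is to assess safety and reactogenicity, with no comparison.

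No section of the protocol defines a difference or a margin, or plans a comparison with earlier CEF recipients.

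**The concern.** Confirming that two products do not differ is a claim of equivalence. It needs a comparator, a definition of how much difference would matter, and enough data to rule that amount out. The protocol provides none of these. Section 3.8 therefore gives the study a property that its own statistics section does not claim.

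The sentence is the protocol's stated reason for running the study as a bridge between the two production methods. If it stands, an uneventful result in 6 people could be cited as demonstrated comparability when the next trial is described to ethics committees, regulators and participants. Such a result would be compatible with a substantial rate of severe reactions.

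**Working it through.** **Is there a figure to reproduce?** No. The sample size of 6 is given without a rate, precision, margin, alpha or power. The check is what 6 volunteers can show. All event rates and margins below are assumptions.

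**1. Upper limit when no event is seen.** With 0 events in n = 6, the exact (Clopper-Pearson) upper limit is 1 − a^(1/6).
- Two-sided 95% (a = 0.025): 1 − 0.025^(1/6) = 0.459, or 45.9%.
- One-sided 95% (a = 0.05): 1 − 0.05^(1/6) = 0.393, or 39.3%.
- For comparison, 1 event in 6 gives an exact 95% interval of 0.4% to 64.1%.

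**2. Chance of missing a reaction entirely.** P(0 of 6) = (1 − p)^6.

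| Assumed true rate p | P(0 of 6) | Expected among 1000 recipients |
|---|---|---|
| 5% | 0.95^6 = 73.5% | 50 |
| 10% | 0.90^6 = 53.1% | 100 |
| 20% | 0.80^6 = 26.2% | 200 |

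A 95% chance of seeing at least one event needs n of at least ln(0.05)/ln(1 − p): 59 volunteers at 5%, 29 at 10% and 14 at 20%.

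**3. An illustration from the protocol.** Section 3.6 reports, in the MVA-EBOZ trial, one volunteer with severe erythema and one with severe fevers, fatigue and malaise; 38 were enrolled. Assume that these are two people and that all 38 received MVA-EBOZ. The rate is then 2/38 = 5.3% (exact 95% interval 0.6% to 17.7%). At 5.3%, P(0 of 6) = (36/38)^6 = 72%. An uneventful result would be the likely outcome even if severe reactions occurred as often as that.

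**4. Would a historical comparison rescue the claim?** Suppose an analysis plan added one. The rows of Table 1 sum to the stated 145 CEF recipients. Exact power of a two-sided 5% Fisher test, 6 against 145:

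| Assumed CEF rate | Assumed new-cell rate | Power |
|---|---|---|
| 5% | 10% | 7.1% |
| 5% | 20% | 23.7% |
| 10% | 30% | 25.2% |
| 10% | 50% | 64.4% |

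Large increases would usually go undetected, so a non-significant result would not show equality.

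**5. Scale of a real no-difference study.** For a two-arm non-inferiority comparison with equal true rates p, one-sided 2.5% and 80% power, n per arm = (1.96 + 0.84)² × 2p(1 − p)/m², computed with unrounded normal quantiles.
- p = 5%: margin m of 10 points, 75 per arm; 20 points, 19 per arm.
- p = 10%: margin of 10 points, 142 per arm; 20 points, 36 per arm.

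These figures show the gap between the claim and the design. They are not a proposed sample size.

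**The case against.** The strongest reply is that the sentence is background. It appears once, in the rationale. The objectives, endpoints and statistics section make no comparative claim, and no test or decision rule implements one. In context, confirming can be read as checking an expectation already formed from earlier use, in a study that the sentence itself calls small. This limits the consequence but does not remove the error: the sentence states what the study is for, and it conflicts with section 10.

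Four stronger readings might be inferred, and the documents do not support them.

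- **That phase IIb rests on proof of comparability from 6 people.** The condition in section 3.8 is only that this trial raises no safety concern, which is weaker than no difference. The section also relies on earlier CEF-produced vaccine and on MVA-EBOZ made on the same cell line.
- **That 6 volunteers are too few.** For a first descriptive look, 6 is consistent with section 10. The adequacy statement in section 5 is measured against objectives worded as assessment, and on that footing it can stand.
- **That missing confidence intervals for each adverse event are a defect.** Interval methods are commonly left to a statistical analysis plan, which is not at hand.
- **That a matched CEF comparator is available.** Table 1 has 40 people aged 18-50 given MVA-NP+M1 first, without a co-administered vaccine, intramuscularly at 1.5 × 10⁸ pfu (FLU002 15, FLU005 13 + 12). But FLU002 was a challenge study whose vaccination-to-challenge interval is not given. The protocol does not show that adverse event terms and collection windows agree. The present dose is converted from TCID50, while Table 1 carries no such qualifier. Even with no events in either group, the Newcombe 95% interval for 0/6 minus 0/40 is −8.8 to +39.0 percentage points.

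**Conclusion.** The claim in section 3.8 is wrong as written. One uncontrolled, descriptive group of 6 cannot confirm that the production change leaves safety unaltered, and no later analysis plan could give it that property. With no events in 6, rates up to 45.9% (two-sided) or 39.3% (one-sided) remain compatible with the data. The limits assume independent volunteers with a common event rate; the 73.5% and 53.1% chances of missing a reaction also rest on assumed rates of 5% and 10%.

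The fault is confined to the stated inference. It touches no endpoint, holding rule or number exposed, and it does not show that the decision to start phase IIb is unsound. It is more than a slip of wording, because it governs what the sponsor may say the study has shown.

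**What to change.** 1. **Section 3.8.** Replace the claim of confirmation with wording such as: *this study will provide initial descriptive safety data, to be viewed alongside earlier experience with the CEF-produced vaccine and with MVA-EBOZ; a difference in safety profile cannot be excluded.*
2. **Section 10.** State the precision of the sample, for example: *if no volunteer has a given event, the exact two-sided 95% upper limit for its true rate is 45.9%; an event with a true rate of 10% would go unseen in 6 volunteers with probability 53.1%.*
3. **Optional.** A side-by-side display with earlier CEF recipients may be added, labelled descriptive. First check that adverse event terms, collection windows, dose units and, for FLU002, the timing of challenge are comparable.

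Items 1 and 2 are text changes. They need no extra volunteers, visits or data. The downside is that the stated claim becomes less favourable.
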